Randomization: Subjects in each of the two age groups (5-17 and ≥ 18 years of age) will be randomized to either the dexamethasone or placebo group (0.3 mg/kg every 12 hours x 4 doses, then tapered). Randomization will be stratified by site, age group, and severity of ACS to preserve balance across treatment groups.

Title of the Protocol: Randomized Trial of Oral Dexamethasone for Acute Chest Syndrome

Data Analyses: We will evaluate the difference in duration of symptoms for ACS between the two treatment groups using a generalized linear mixed model (GLMM). Here, the natural log of the duration of symptoms will act as the dependent variable of interest and the treatment status as the grouping factor. As a secondary analysis, the duration of hospitalization, supplemental oxygen, and fever will be analyzed in a similar manner. Laboratory parameters will be analyzed using a GLMM model, with treatment group, baseline laboratory value, age group, severity, and site as fixed effects and subject as a random effect. Clinical endpoints and AEs will be summarized by treatment and analyzed for differences across treatment group. Two formal interim analyses will be performed on the primary efficacy variable. The first interim analysis will take place when 56 subjects have resolved signs and symptoms of ACS OR have been discharged from the hospital. In this interim analysis, the primary efficacy hypothesis will be tested at the $\alpha = 0.001$ level. The study will be stopped if significant efficacy is identified. The second interim analysis will be performed when 112 subjects have resolved signs and symptoms of ACS OR have been discharged from the hospital. The primary efficacy hypothesis will be tested at the $\alpha = 0.01$ level. If significant efficacy is identified for total subjects and for children, the study will be stopped. Otherwise, the study will continue enrollment to 112 children, after which the primary efficacy hypothesis will be tested on the $\alpha = 0.039$ level.

Human Subjects: Potential risks include avascular necrosis, vaso-occlusive crisis, mood changes, hypertension, nausea, vomiting, dyspepsia, gastric ulceration, delayed wound healing, acne, and infection.

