7.1.2 Description of Type of Study

This is a multi-center, randomized, double-blind, placebo-controlled Phase III clinical trial that will include at least 56 subjects with SCD who are hospitalized for ACS. Individuals who meet entry criteria will be randomized to receive either dexamethasone or placebo. Dexamethasone will be administered initially as 0.3 mg/kg by mouth every 12 hours for a maximum of 4 doses (2 days) or until discharge from the hospital, whichever occurs first. Afterward, the study drug will be tapered over 6 days for a total duration of therapy not to exceed 8 days. Due to possible age-related and ACS severity-related differences in the duration of signs and symptoms of ACS, randomization will be stratified by age and severity of ACS (see Section 8.3). We are enrolling a maximum of 112 pediatric subjects. We will enroll adult subjects at the rate site participation will allow, which we anticipate will be no more than 56 subjects. Interim analyses will be performed when a total of 56 subjects and 112 subjects have completed their hospital stay. If we do not stop enrollment after these interim analyses are completed, we will continue to enroll up to a maximum total of 112 pediatric subjects. The efficacy and safety of dexamethasone will be compared to placebo in the context of standard supportive care for ACS.

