8.3 Stratification

Before randomization, subjects will be stratified by site, age (< 18 years or ≥ 18 years) and by severity of ACS (defined below). Stratification by age and severity of ACS will be done to ensure balance across treatment groups. Strata will not be adequately sized (i.e., powered) to analyze the primary endpoint in each stratum.

Mild to moderately severe ACS is defined by all the diagnostic criteria for ACS listed in the subject eligibility section in addition to the following:

- transcutaneous oxygen saturation of ≥ 85% in room air, and
- segmental or lobar infiltrates that involve no more than two lobes by chest radiography.

Severe ACS is defined by all the diagnostic criteria for ACS listed in the subject eligibility section and one or more of the following:

- impending respiratory failure or need for invasive or non-invasive ventilatory support,

- transcutaneous oxygen saturation of $< 85\%$ in room air or $\leq 90\%$ despite maximal supplemental oxygen, or
- segmental or lobar infiltrates that involve three or more lobes by chest radiography.

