13.2.2 Efficacy Analyses

All efficacy analyses will be performed on the ITT population while the primary and some secondary analyses will be repeated on the per-protocol population. Center will be included in the models as permitted by sample size. Center will be eliminated from the models if it appears to be an insignificant variable in the model.

The primary analysis will compare the duration of ACS signs and symptoms (as assessed by the ACS assessment, Appendix3) or the duration of hospitalization for ACS, whichever happens first, of subjects in the dexamethasone treated arm to those in the placebo treated arm. The symptom/hospitalization duration for subjects with ACS will be summarized by treatment group, severity strata, and age strata. The effect of treatment on symptom/hospitalization duration will be tested using a Generalized Linear Mixed Model (GLMM) with the natural log of symptom/hospitalization duration as the outcome variable. The SAS[®] procedure MIXED will be used to fit the GLMM. The GLMM will include treatment, age group, and severity as fixed effects. The GLMM will not specify any variables as random effects or repeated effects, but it will use the GROUP option in the REPEATED statement to estimate separate error variances for each treatment (i.e., GROUP = “treatment”). The SAS[®] procedure MIXED will be used to fit the GLMM.

The GLMM model specified above is necessary for the primary analysis because pilot data give evidence that the length of stay (LOS) in the hospital (which is assumed to be similar to duration of symptoms) for ACS has a lognormal distribution. If the LOS for ACS is distributed as lognormal in each treatment group, then the model of the natural log of LOS must allow for differences in treatment group variances as well as for treatment group mean differences. By allowing for differences in treatment group variances and treatment group means, the treatment group specific distributions can be correctly estimated under the lognormal assumption, resulting in a correct comparison of treatment group means.

As a secondary analysis, parametric survival analysis techniques will be used to estimate distributional parameters and model the hazard function of symptom duration/LOS/hypoxemia/fever for each treatment group. The time to the event of interest (e.g., symptom duration) will be described using a Kaplan-Meier plot stratified by treatment.

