13.2.4 Interim Analyses

Two formal interim analyses will be performed on the primary efficacy variable. The first interim analysis will take place when 56 subjects have resolved signs and symptoms of ACS *or* have been discharged from the hospital. To test for differences between the treatment arms, the same F-test from the GLMM specified in the primary analysis will be used with a Peto stopping boundary of $p < 0.001$.⁷⁸ The study will be stopped if significant efficacy is identified. The second interim analysis will be performed when 112 subjects have resolved signs and symptoms of ACS *or* have been discharged from the hospital. The primary efficacy hypothesis will be tested at the $\alpha = 0.01$ level on the total subjects,

and the 0.05 level for the children. If significant efficacy will be identified for total subjects and for children, the study will be stopped. Otherwise, the study will continue enrollment to 112 children, after which the primary efficacy hypothesis will be tested on the $\alpha = 0.039$ level. By utilizing these alpha levels for each test and a step-down procedure for the pediatric sub-population, the overall study alpha level for the test of the primary hypothesis remains at the 0.05 level.

In order to ensure that future subjects are not exposed to study drug unnecessarily, the DSMB will also be provided with the conditional probability of completing a successful trial at the interim analyses under three scenarios: (1) the treatment difference continues to be the same as in the first portion of the trial; (2) the treatment difference is zero for the next portion of the trial; (3) the treatment difference is 30 hours for the next portion of the trial. Based on this information, the DSMB can make an informed decision about the futility of the trial.

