13.3 Statistical Considerations

13.3.1 Covariates

Age group and severity group will be used as covariates in the primary analysis. Baseline laboratory measurements will be controlled for when analyzing laboratory outcomes. Center will be included in the models as permitted by sample size. Other covariates may be considered in the analysis of clinical, laboratory, and safety outcomes as needed.

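### The primary model adjusts for age only as under 18 versus 18 and over, which may forgo a little precision among children; prespecifying age in years is a minor, nearly free improvement

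*Protocol*

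**What the plan says.** Section 13.2.2 gives the primary model for log duration: "The GLMM will include treatment, age group, and severity as fixed effects". Each treatment has its own error variance, and center is included if sample size permits. Section 13.3.1 repeats the choice: "Age group and severity group will be used as covariates in the primary analysis". That section allows other covariates as needed but names none.

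Section 8.3 defines the age factor: "subjects will be stratified by site, age (< 18 years or ≥ 18 years) and by severity of ACS". The synopsis uses the same split, and Section 9.2 makes age group, site and severity the minimization factors.

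Section 7.1.2 gives the expected mix: "We are enrolling a maximum of 112 pediatric subjects", with adults enrolled as sites allow, "which we anticipate will be no more than 56 subjects". It justifies stratifying by "possible age-related and ACS severity-related differences in the duration of signs and symptoms of ACS".

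Section 13.2.4 tests all subjects at the second interim analysis at 0.01 "and the 0.05 level for the children". The trial stops at that look only if both tests succeed. The section names the primary-analysis F-test for the first interim analysis and does not state the model for the children-only test.

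**The concern.** A two-level factor split at 18 is the same for every subject aged 5 to 17. If 112 children and 56 adults are enrolled, it is constant for two thirds of the sample. In a children-only analysis with the same covariates it drops out, leaving severity and possibly center. Minimization does not balance age within childhood either.

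If log duration changes with age within 5 to 17 years, that variation stays in the residual although age is available for every subject. The cost would be a somewhat wider confidence interval and some lost power. It would matter most in the children-only test, which has the fewest subjects and is one of the two conditions for stopping at the second look.

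**Working it through.** **Inputs from the protocol (Section 13.4).** Mean log duration 4.25 on placebo and 3.95 on dexamethasone, so the difference is 0.30. Standard deviations (SDs) on the log scale 0.6 and 0.3; two-sided alpha 0.05; power 90%; Satterthwaite t-test with equal group sizes. Section 13.2.4 gives alpha 0.039 for the final test.

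**Reproducing the plan's figure.** The standard error is SE = √[(0.6² + 0.3²)/n]. At n = 54 per arm, SE = √(0.45/54) = 0.0913, the noncentrality is 0.30/0.0913 = 3.29, and the Satterthwaite degrees of freedom are 77.9. Noncentral-t power is 90.1%; at n = 53 it is 89.5%. The stated 54 per group therefore reproduces. It contains no covariate adjustment, so it does not depend on how age is coded.

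**What the two-level term already captures.** Section 5 gives an overall mean stay of about 7 days, with children about 3 days shorter than adults. Assume two thirds are children:

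- The means are 7 − 3 × 1/3 = 6 days for children and 9 days for adults, so the log ratio is ln(9/6) = 0.405.
- The between-group variance is (2/3)(1/3)(0.405²) = 0.036.
- The average planning variance is (0.36 + 0.09)/2 = 0.225.
- The share explained is 0.036/(0.036 + 0.225) = 14%.

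The term is therefore useful across the whole sample. Within children it explains nothing.

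**Effect of adding age in years.** Let r be the correlation of age with log duration, given age group and severity. The protocol gives no value, so r is an assumption, taken to be equal in both arms. Each residual SD is multiplied by √(1 − r²), so residual variance falls by r²: 1%, 4%, 9% and 16% for r = 0.1, 0.2, 0.3 and 0.4. The loss of one degree of freedom is ignored.

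| Setting | r = 0 | 0.1 | 0.2 | 0.3 | 0.4 |
|---|---|---|---|---|---|
| 54 per arm, alpha 0.05 | 90.1% | 90.4% | 91.2% | 92.5% | 94.3% |
| 84 per arm, alpha 0.039 | 97.7% | 97.8% | 98.1% | 98.6% | 99.1% |
| Children only, 40 per arm, alpha 0.05 | 79.4% | 79.8% | 81.0% | 83.0% | 85.9% |
| Children only, 37 per arm, alpha 0.05 | 76.1% | 76.6% | 77.8% | 79.9% | 83.0% |

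The 84 per arm is (112 + 56)/2, the largest size the protocol anticipates. The 37 per arm is two thirds of 112, halved, and 40 is a nearby alternative. Both child counts are assumptions, because the protocol does not fix the split at the second interim analysis.

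**How strong an age effect each r implies.** If ages are uniform over 5 to 18, the SD of age is 13/√12 = 3.75 years. With a log-duration SD of √0.225 = 0.474, the slope is r × 0.474/3.75 per year. If duration lengthens with age, ten years of age then means about 13%, 29%, 46% or 66% longer duration at r = 0.1, 0.2, 0.3 or 0.4. The protocol reports no such gradient.

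**The case against.** The strongest reply is that nothing in the protocol shows duration varying with age among children. The only age contrast given for duration is child versus adult, and the two-level term captures it. This stands, so lost precision is a possibility and not a demonstrated fact.

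A reader might infer that age variation is built into the endpoint, because the respiratory-rate limit in Appendix 3 falls from 30 to 25 at age 12 and the pain instrument changes at about age 10. The documents do not support this. The rate limits are age-specific upper limits of normal, which tend to remove age dependence. Both pain instruments use a 0 to 10 scale with the same threshold of 4, and the saturation criterion is set against the subject's own steady state where that is known.

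A reader might also infer that the analysis is biased or its type I error inflated. It is neither. Adjusting for the minimization factor as coded is standard practice, and the confidence interval already allows for chance imbalance in other covariates. The pilot SDs came from studies of children and so already include any age variation present in those samples.

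Nor is it established that severity alone would remain in the children-only test. Center may enter, other covariates are permitted, and the model for that test is not stated. A statistical analysis plan might name age. The structural fact still stands: the protocol fixes age in the primary model as a two-level factor and commits to nothing finer.

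**Conclusion.** This is a minor efficiency improvement, not an error. The age term is constant among children and would contribute nothing to the children-only test if the primary model is reused there. The gain from adding age in years depends wholly on r, which is unknown. At r = 0 there is none. For r from 0.1 to 0.4 the gain is:

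- about 0.3 to 4.2 points at 54 per arm;
- about 0.1 to 1.4 points at 84 per arm and alpha 0.039;
- about 0.4 to 7 points in a children-only test with 37 to 40 per arm.

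These figures rest on the planning means and SDs, a linear effect of age equally strong in both arms, and the assumed group sizes. The stronger statement that the plan wastes precision goes beyond the documents.

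**What to change.** In Sections 13.2.2 and 13.3.1, keep age group as the minimization factor and model term, and add age at enrollment in years as a prespecified linear fixed effect. State in Section 13.2.4 that the children-only test uses the same model without age group, so that age in years and severity remain.

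The change is a few words of text and one model degree of freedom, with no new data collection. If age is unrelated to duration within the groups, nothing is gained and essentially nothing is lost. The wording should be settled before any unblinded interim look, because a covariate chosen later under the open clause in Section 13.3.1 would be open to challenge.

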Based on these preliminary findings, we anticipate that dexamethasone will decrease the LOS by 30 hours (compared to 33 hours for Bernini and 27 hours for Huh) and we will therefore power our tests to detect a 30-hour difference. The data from Huh et al (2004)⁴⁸ gives evidence that the LOS for ACS may have a lognormal distribution, but the clinical hypothesis makes a statement about differences in mean of LOS not the natural log of LOS. Assuming the LOS in each treatment group is distributed as lognormal, normal distribution based statistical analysis methodologies can be used for analysis of the natural log of LOS. With the lognormal assumption, the mean LOS for each treatment group is a function of both the mean and variance of the natural log of LOS, so the following sample size calculations had to consider possible lognormal distributions and the mean difference on the untransformed scale.

Table 13.2 presents the lognormal transformed results of Table 13.1, which we used in the sample size calculations.

Table 13.2 Effect of dexamethasone on natural log of the duration of hospitalization for ACS in children

	Bernini et al, (1998) Ln(Duration of hospitalization)	Huh et al (2004) Ln(Duration of hospitalization)
Placebo	4.217 (SD=0.574)	4.216 (SD=0.707)
Dexamethasone	3.795 (SD=0.331)	3.954 (SD=0.560)

The hypothesis tested is: shortened duration of ACS signs and symptoms/hospitalization by at least 30 hours for children with SCD who are hospitalized for the treatment of ACS and receive dexamethasone. Using LOS as a surrogate, we used a two group Satterthwaite t-test of equal means (unequal variances, equal n's) to test the difference in natural log of the hospitalization duration between treatment groups. We additionally

assumed a two-sided alpha of 0.05 and 90% power. Several scenarios were explored in which we varied the lognormal variance parameter and lognormal mean parameter for the two treatment groups according to the ranges found in the two pilot studies.

If we assume that

- we are testing a two-sided hypothesis,
- the treatment effects seen in children are the same in adults,
- the lognormal population standard deviation for the placebo group is 0.6,
- the lognormal population standard deviation of the dexamethasone group is 0.3,
- the lognormal mean of the placebo group is 4.25,
- the lognormal mean of the dexamethasone group 3.95, (corresponding to a mean difference in LOS between the two treatment groups of 30 hours),

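### The primary F-test compares log-means, while Section 13.4 puts the hypothesis on mean hours; the claim of a correct comparison of means is wrong when the log-SDs differ, and the mismatch costs power

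*Protocol*

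**What the plan says.** Section 13.4 (Sample Size) says that "the clinical hypothesis makes a statement about differences in mean of LOS not the natural log of LOS", and notes that a lognormal mean depends on both the mean and the variance of the logged values. It then words the hypothesis this way: "The hypothesis tested is: shortened duration of ACS signs and symptoms/hospitalization by at least 30 hours". The sample size itself comes from a Satterthwaite t-test on log length of stay.

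Section 13.2.2 (Efficacy Analyses) fits the primary model "with the natural log of symptom/hospitalization duration as the outcome variable". It uses the GROUP option "to estimate separate error variances for each treatment" and concludes that the arm distributions "can be correctly estimated under the lognormal assumption, resulting in a correct comparison of treatment group means".

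Section 13.2.4 (Interim Analyses) fixes the statistic: "the same F-test from the GLMM specified in the primary analysis will be used". One of the conditional-probability scenarios for the DSMB assumes that "the treatment difference is 30 hours for the next portion of the trial".

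No section gives a test or contrast for mean hours.

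**The concern.** For a lognormal duration with log-mean mu and log-variance s², mean hours equal exp(mu + s²/2). The treatment F-test asks only whether the two mu are equal. Fitting a separate variance per arm makes the standard error and degrees of freedom right for that question, but it does not put s² into the hypothesis. Hypothesis and test coincide only if the log-variances are equal, and the protocol plans on their being unequal.

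This is the single confirmatory hypothesis (Section 13.3.3), and it is tested at every look. At stake are the scale on which the trial may state its conclusion and the power for the effect that Section 13.4 says is of interest. Two smaller problems follow. The 30-hour figure is worded as the tested hypothesis, although the null is no difference. And the 30-hour conditional-power scenario has no single value on the scale that is tested.

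**Working it through.** **Inputs (Section 13.4).** Log-means 4.25 (placebo) and 3.95 (dexamethasone); log-SDs 0.6 and 0.3; two-sided alpha 0.05; 54 per arm, or 56 with the allowance for withdrawals. Other SD pairs in the protocol are 0.574/0.331 (1998 pilot, Table 13.2), 0.707/0.560 (follow-up pilot, Table 13.2) and 0.6/0.5 (upper limits of the alternative scenarios). The calculations leave out the age and severity covariates and take the SDs as residual SDs.

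**1. The plan's own figures reproduce.** Mean hours are exp(4.25 + 0.18) = 83.9 and exp(3.95 + 0.045) = 54.3, a difference of 29.6, stated as 30. For the Satterthwaite test, SE = √((0.36 + 0.09)/54) = 0.0913 and the noncentrality is 0.30/0.0913 = 3.29. Power is 90.07% at 54 per arm and 89.5% at 53. The stated 54 is therefore right for the log-scale test.

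**2. The part of the effect that the test cannot see.** With both log-means at 4.25, mean hours are 83.9 and exp(4.25 + 0.045) = 73.3. The 10.6-hour difference is due to variance alone, and the F-test rejects there only at its nominal level. The remaining 19.0 hours come from the log-mean. In hours the split depends on the order: with both log-means at 3.95 the variance part is 62.2 − 54.3 = 7.9. On the log scale it does not: (0.36 − 0.09)/2 = 0.135 out of 0.30 + 0.135 = 0.435, or 31%.

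**3. Power at 54 per arm.** The comparison is a Wald test of (muP + varP/2) − (muD + varD/2), with SE² = Σ(s² + s⁴/2)/n.

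- Planning values: SE² = (0.36 + 0.0648 + 0.09 + 0.00405)/54 = 0.00961, so SE = 0.0980. 0.435/0.0980 = 4.44, which gives power 99.3%, against 90.1% for the F-test.
- Follow-up pilot values (4.216/3.954, SDs 0.707/0.560): the contrast is 0.262 + 0.093 = 0.355 and SE = 0.135, which gives power 74.7%, against 56.1% for the F-test.

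**4. F-test when mean hours are equal.** This requires the dexamethasone log-mean to exceed placebo's by (sP² − sD²)/2. Rejection at 56 per arm, two-sided 0.05:

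| Log-SDs | Log-mean gap | Rejection |
|---|---|---|
| 0.6 / 0.3 | 0.135 | 31.9% |
| 0.574 / 0.331 | 0.110 | 23% |
| 0.707 / 0.560 | 0.093 | 12% |
| 0.6 / 0.5 | 0.055 | 8% |

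Simulation of the first row (100,000 trials) also gave 31.9%: 31.8% favoured placebo and 0.04% favoured dexamethasone. The contrast in step 3 had a simulated size of 5.4% in the same setting. At the interim levels the first-row figure is about 1% (28 per arm, 0.001) and 14% (56 per arm, 0.01). If enrolment reached 112 children and 56 adults, 84 per arm, it would be 41% at 0.039. That total is an assumption; Section 7.1.2 only anticipates the adult number.

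**5. The 30-hour scenario on the log scale.** With placebo at 4.25 and SD 0.6, a 30-hour benefit means a dexamethasone mean of 53.9 hours. The log-mean difference is then 0.31, 0.39 or 0.44 for a dexamethasone SD of 0.3, 0.5 or 0.6.

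**The case against.** A reader might take the 32% as a one-in-three chance of falsely declaring dexamethasone effective. The documents do not support that. Nearly all of those rejections show dexamethasone with the longer geometric mean. The scenario needs dexamethasone to halve the log-SD while raising the median by 14% (exp(0.135) = 1.145), whereas in both pilots log-mean and log-SD fell together. If the two distributions are identical, the test holds its level.

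A reader might also infer that the F-test says nothing about mean hours. That goes too far. Under lognormality, a lower log-mean with an SD no larger than placebo's implies fewer mean hours, and in every SD pair listed above dexamethasone has the smaller SD. For a benefit claim, the F-test is then conservative.

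It can further be said that the Synopsis states the null simply as no difference in duration and names log duration as the dependent variable, that sample size and test agree with each other, and that the 30 hours is loose wording for a planning effect. All of this is fair, and it limits the point to wording, estimand and power. It does not rescue the sentence in Section 13.2.2, which presents the model as a comparison of means, or reconcile it with Section 13.4, which places the hypothesis on mean hours and not on their logarithm.

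Finally, testing lognormal means is itself a choice of estimand: with equal medians and SDs 0.6/0.3, that contrast declares a benefit in about 28% of simulated trials, from variance alone. Mean or median duration is for the sponsor to decide.

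**Conclusion.** The point stands as a mismatch between the stated hypothesis and the test, with a loss of power for that hypothesis. At the planning values the loss is about 9 percentage points at 54 per arm (90% against 99%); at the follow-up pilot's values it is about 19 (56% against 75%). The rejection rate at equal mean hours runs from 8% to 32% over the protocol's SD pairs, at 56 per arm and alpha 0.05, almost entirely in placebo's favour. It is not an inflated risk of a false efficacy claim. The sample size of 54 is correct for the log-scale test as specified.

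These figures assume lognormal durations, equal allocation, and SDs unchanged by covariate adjustment. The contradiction in the text does not depend on them, beyond the log-SDs being unequal.

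**What to change.** Settle one scale before any unblinded analysis, because choosing afterwards would be post hoc.

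- **Keep the F-test.** State the primary hypothesis and conclusion as a ratio of geometric means, and delete the clause in Section 13.2.2 about a correct comparison of means.
- **Or target mean hours.** Make the primary contrast (muP + varP/2) − (muD + varD/2) from the same PROC MIXED fit, with a standard error that includes the uncertainty in the variance estimates. State how hours are standardised over age group and severity, since effects that are additive on the log scale give a different number of hours in each stratum.

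In either case, describe 30 hours in Section 13.4 as the planning effect and not as the tested hypothesis. In Section 13.2.4, give the SDs and placebo mean used to convert the 30-hour conditional-power scenario to the tested scale.

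The cost is protocol and SAP wording and, for the second option, a few lines of code. No additional patients are needed.
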